7.4.3 Pharmacokinetic parameters

Handling of missing PK data will be performed according to the relevant SOP of the Sponsor [\[001-MCS-36-472\]](#).

For the non-compartmental analysis, concentration data identified with NOS, NOR or NOA will generally not be considered. Concentration values in the lag phase identified as BLQ or NOP will be set to zero. All other BLQ/NOP values of the profile will be ignored. The lag phase is defined as the period between time zero and the first time point with a concentration above the quantification limit.

7.5 RANDOMISATION

Randomisation is not applicable in this open-label, single arm study. All subjects will receive the same treatment. Consecutive subject numbers will be assigned via the EDC system.

7.6 DETERMINATION OF SAMPLE SIZE

For this clinical trial, no prospective calculations of statistical precision or power have been made. The planned sample size of 6 subjects is judged as being adequate to get reliable results regarding the trial objectives.

The sample size of 6 subjects accounts for moderate PK variability, the potential of the drug to induce vomiting and potential drop-outs. For replacement rules, refer to [Section 3.3.5.](#)

8. INFORMED CONSENT, DATA PROTECTION, TRIAL RECORDS

The trial will be carried out in compliance with the protocol, the principles laid down in the Declaration of Helsinki, in accordance with the ICH Harmonised Tripartite Guideline for Good Clinical Practice (GCP), and relevant BI SOPs.

The Investigator should inform the Sponsor immediately of any urgent safety measures taken to protect the study subjects against any immediate hazard, and also of any serious breaches of the protocol or of ICH GCP.

The rights of the Investigator and of the Sponsor with regard to publication of the results of this trial are described in a separate agreement between the Investigator or the trial site and the Sponsor. As a general rule, no trial results should be published prior to finalisation of the CTR.

8.1 STUDY APPROVAL, SUBJECT INFORMATION, AND INFORMED CONSENT

This trial will be initiated only after all required legal documentation has been reviewed and approved by the respective Institutional Review Board (IRB) / Independent Ethics Committee (IEC) and competent authority (CA) according to national and international regulations. The same applies for the implementation of changes introduced by amendments.

Prior to a subject's participation in the trial, written informed consent must be obtained from each subject (or the subject's legally accepted representative) according to ICH GCP and to the regulatory and legal requirements of the participating country. Each signature must be personally dated by each signatory and the informed consent and any additional subject information form are to be retained by the investigator as part of the trial records. A copy of the signed and dated written informed consent and any additional subject information must be given to each subject or the subject's legally accepted representative.

The subject must be informed that his personal trial-related data will be used by Boehringer Ingelheim in accordance with the local data protection law. The level of disclosure must also be explained to the subject.

The subject must be informed that his or her medical records may be examined by authorised monitors (Clinical Monitor Local/Clinical Research Associate) or Clinical Quality Assurance auditors appointed by Boehringer Ingelheim, by appropriate IRB/IEC members, and by inspectors from regulatory authorities.

8.2 DATA QUALITY ASSURANCE

A quality assurance audit/inspection of this trial may be conducted by the Sponsor or sponsor's designees, by IRBs/IECs, or by regulatory authorities. The quality assurance auditor will have access to all medical records, the Investigator's trial-related files and correspondence, and the informed consent documentation of this clinical trial.

Proprietary confidential information © 2018 Boehringer Ingelheim International GmbH or one or more of its affiliated companies

The data management procedures to ensure the quality of the data are described in detail in the trial data management and analysis plan (TDMAP) available in the TMF.

8.3 RECORDS

CRFs for individual subjects will be provided by the Sponsor. For drug accountability, refer to [Section 4.1.8](#).

8.3.1 Source documents

Source documents provide evidence for the existence of the subject and substantiate the integrity of the data collected. Source documents are filed at the Investigator's site.

All data reported in the CRFs must be consistent with the source data or the discrepancies must be explained.

The Investigator may need to request previous medical records or transfer records, depending on the trial.

8.3.2 Direct access to source data and documents

The Investigator/institution will permit trial-related monitoring, audits, IRB/IEC review and regulatory inspection, providing direct access to all related source data/documents. CRFs and all source documents, including progress notes (if applicable) and copies of laboratory and medical test results must be available at all times for review by the Sponsor's clinical trial monitor, auditor and inspection by health authorities (e.g. FDA). The Clinical Research Associate/on site monitor and auditor may review all CRFs, and written informed consents. The accuracy of the data will be verified by reviewing the documents described in [Section 8.3.1](#).

8.3.3 Storage period of records

Trial site:

The trial site must retain the source and essential documents (including ISF) according to the national or local requirements (whatever is longer) valid at the time of the end of the trial.

Sponsor:

The Sponsor must retain the essential documents according to the Sponsor's SOPs.

8.4 EXPEDITED REPORTING OF ADVERSE EVENTS

BI is responsible to fulfil their legal and regulatory reporting obligation in accordance with regulatory requirements.

8.6 COMPLETION OF TRIAL

The EC/CA in each participating EU member state needs to be notified about the end of the trial (last subject/subject out, unless specified differently in [Section 6.2.3](#) of the CTP) or early termination of the trial.

10. APPENDICES

10.1 RADIO BURDEN CALCULATION

Radiation Burden Calculation Report
BI730357 ADME-V2

Radiation Burden Calculation Report

Title (provisional)	A phase I, open-label, single-dose trial to investigate metabolism and pharmacokinetics of BI 730357 BS (C-14) administered as oral solution in healthy male volunteers
Sponsor:	Boehringer Ingelheim
Protocol No:	BI1407-0031
PRA Project Id:	BID015EC-180155
Version Date:	05 July 2018

Calculation of Radiation Burden (Dosimetry)

BI 730357 is a new chemical entity Retinoic acid-related Orphan Receptor- γ (ROR γ t) antagonist, in development for the treatment of patients with psoriasis, psoriatic arthritis, ankylosing spondylitis, asthma, and inflammatory bowel disease. ROR γ t is a nuclear hormone receptor/transcription factor expressed in distinct subsets of lymphoid cells. Upon cell activation, in response to multiple activation signals including cytokines and T cell receptor engagement, ROR γ t regulates the transcription of IL-17A, IL-17F, IL-22 genes, and of the IL-23 receptor gene.

Excretion and pharmacokinetic studies using BI 730357 were conducted on rats^{1,3}, and quantitative tissue distribution studies on pigmented rats². A radiation dose assessment was made based on these studies. In addition, data from the Investigator Brochure⁴ were taken into consideration.

The following assumptions, based on the data from these experiments, and taking the worst-case scenario, were made to be able to estimate the effective radiation dose:

- After oral dosing, BI 730357 and possible metabolites are considered to be distributed more or less homogeneously throughout the body, with the exception of higher exposure of the liver, which is calculated separately.
- The major part of the administered amount of ¹⁴C-radiolabeled BI 730357 and possible metabolites show reasonably slow, bi- and triphasic elimination from the body, mostly via fecal and for a smaller part via urinary excretion. For this estimation, the longest elimination half-life given for whole blood or plasma was used.
- Using the data of the BI 730357 study in rats a half-life of total ¹⁴C-activity of 64 hours is estimated. In humans a terminal phase half-life of BI 730357 of approximately 28 hours is assumed³. In the current estimation a half-life of total radioactivity of 64 hours is used.
- The absorbed fraction is assumed to be 1, based on a study on the biliary and intestinal excretion in the rat³, which gave a number of 94%.
- Based on the excretion study in rats³ ¹⁴C-radiolabeled BI 730357 is found to be excreted both in feces and in urine. For the calculation is assumed: 86% of the administered radioactivity is excreted via the gastrointestinal tract in feces and 14% is excreted via the kidneys in urine.

Based on these assumptions the estimated effective radiation burden after a single oral radioactivity dose of 3.7 MBq ¹⁴C-radiolabeled BI 730357 is approximately 0.14 mSv. For biomedical investigations in small groups of human volunteers an effective dose of 0.1 – 1.0 mSv is considered acceptable⁵.

References:

- 1: Excretion of radioactivity in urine, feces and bile after oral and intravenous administration of [14C]-BI 730357 to rats, 03Nov17
- 2: Quantitative whole-body autoradiography in male pigmented rats after single iv or oral administration of [14C]BI 730357 27Mar18
- 3: Investigation of intestinal secretion and biliary excretion of radioactivity after iv administration of [14C]BI 730357 to rats 16Feb18
- 4: Investigator's brochure Version 3 dated 28 June 2017.
- 5: Recommendations of the International Commission on Radiological Protection. User's ICRP publication 60, Pergamon Press 1992 and update from ICRP 103.

Appendix A1: Radiation burden of the gastrointestinal tract after oral administration of 3.7 MBq ^{14}C BI 730357

Using SEE-values, an organ-specific radiation burden can be estimated. The SEE-value is dependent, among other factors, on the mass of the target organ and the type of radiation.

With these SEE-values and the number of disintegrations U in the target organ, the organ dose equivalent H_i is calculated:

$H_i = \text{constant} \times U \times \text{SEE}$ (mSv); using a target organ-related weight factor, the contribution of the organ burden to the body burden is translated as: $H_{w,i} = H_i \times \text{weight factor}$ (mSv).

In order to be able to calculate the radiation burden of the GI tract, this has been divided in five sections, i.e., the stomach (st), the small intestines (si), the right part of the large intestines, the left part of the large intestines (lc) and the rectum / sigmoid (rs).

The SEE-values for these organs are:

ST:	1.0×10^{-5}	(weight factor = 0.12)
SI:	3.2×10^{-7}	(weight factor = 0.01)
RC:	2.3×10^{-10}	(weight factor = 0.048)
LC:	2.9×10^{-10}	(weight factor = 0.045)
RS:	9.2×10^{-10}	(weight factor = 0.027)

The number of disintegrations U in each target organ depends on the amount of radioactivity excreted, or any metabolites that are eliminated via the gall bladder that is standardised for the various compartments of the GI tract (constant). $I_0 = 3.7 \text{ MBq}$; excretion via GI tract: 86% of the dose, excretion via urine: 14% of the dose. These assumptions give:

H _{st} =	0.0030 mSv
H _{si} =	0.0000 mSv
H _{rc} =	0.0000 mSv
H _{lc} =	0.0000 mSv
H _{rs} =	0.0000 mSv
total GI:	0.0030 mSv

The total contribution of the GI tract to the effective dose (body radiation burden) amounts to 0.0030 mSv.

Appendix A2: Radiation burden of the central compartment after oral administration of 3.7 MBq ^{14}C BI 730357

Average body weight = 70 kg; SEE = 7.1905×10^{-7} ; 88% of the dose administered orally and excreted with a half-life of 64 hours. Total number of disintegrations in the central compartment after oral administration of 3.7 MBq [^{14}C] BI 730357 is 1072×10^9 with a tissue weighting factor of 0.96 giving a $H_{w,i}$ of 0.1152 mSv.

Appendix A3: Radiation burden of the liver after oral administration of 3.7 MBq ^{14}C BI 730357

For the Liver SEE = 2.72×10^{-5} ; 12% of the dose administered orally excreted by the liver with a half-life of 53 h. The weighting factor for the liver is 0.04, the contribution to the radiation burden is 0.0211 mSv.

The total effective dose (radiation burden), based on the above-mentioned worst-case scenario amounts to $0.0030 + 0.1152 + 0.0211 = 0.14 \text{ mSv}$.

Name and Date:

Signature:

05 July 2018

11. DESCRIPTION OF GLOBAL AMENDMENT(S)

Number of global amendment		1
Date of CTP revision		25 September 2018
EudraCT number		2018-001837-41
BI Trial number		1407-0031
BI Investigational Product(s)		BI 730357
Title of protocol		A phase I, open-label, single-dose trial to investigate metabolism and pharmacokinetics of BI 730357 BS (C-14) administered as oral solution in healthy male volunteers
To be implemented only after approval of the IRB / IEC / Competent Authorities		
To be implemented immediately in order to eliminate hazard – IRB / IEC / Competent Authority to be notified of change with request for approval		
Can be implemented without IRB / IEC / Competent Authority approval as changes involve logistical or administrative aspects only		
Section to be changed	3.3.5 5.2.3 5.2.5.1 5.5.2.5	Exclusion Criteria Assessment of safety laboratory parameters Vital signs Urine sampling
Description of change	3.3.5 5.2.3 5.2.5.1 5.5.2.5	Deleted the number before sentence “In addition, the following trial-specific exclusion criteria apply” Deleted the sentence “(please specify which)” and deleted the timepoint Day 1, 1:00 in the footnote for lab set C in table 5.2.3: 1 Changed the type of monitor used for blood pressure measurements Added “at least” in front of “0.05 % Tween 20”
Rationale for change	3.3.5	The incorrect numbering in the list of exclusion criteria was corrected. The exclusion criteria per

Proprietary confidential information © 2018 Boehringer Ingelheim International GmbH or one or more of its affiliated companies

Number of global amendment		1
	5.2.3	se were not changed. The type of alcohol test is specified in the next paragraph; the deleted sentence was a leftover from protocol drafting process Inconsistency in the footnote: Timepoint Day 1, 1:00 for safety lab is not in the Flow Chart since it is not necessary for safety reasons.
	5.2.5.1	Site has changed the equipment since old monitor has become obsolete
	5.5.2.5	The concentration of Tween 20 in the urine container is now allowed to be 0.05% or higher.

APPROVAL / SIGNATURE PAGE

Document Number: c22159106

Technical Version Number: 2.0

Document Name: clinical-trial-protocol-revision-01

Title: A phase I, open-label, single-dose trial to investigate metabolism and pharmacokinetics of BI 730357 BS (C-14) administered as oral solution in healthy male volunteers

Signatures (obtained electronically)

2. LIST OF ABBREVIATIONS

Term	Definition / description
ADPC	Proper name of the analysis dataset containing PK concentrations per time-point or per time-interval
ADPP	Proper name of the analysis dataset containing calculated PK parameters
ADS	Analysis dataset
AE	Adverse Event
AESI	Adverse event of special interest
ALT	Alanine aminotransferase
AST	Aspartate aminotransferase
AUC _{0-tz}	Area under the concentration-time curve of the analyte in plasma over the time interval from 0 to the last quantifiable data point
BI	Boehringer Ingelheim
BLQ	Below the lower limit of quantification
BMI	Body Mass Index
BP	Blood Pressure
BRPM	Blinded Report Planning Meeting
C _{max}	Maximum measured concentration of the analyte in plasma
CTP	Clinical Trial Protocol
CTR	Clinical Trial Report
CV	Arithmetic coefficient of variation
ECG	Electrocardiogram
EDC	Electronic Data Capture
FAS	Full Analysis Set
fe _{faeces, 0-t₂}	fraction of [¹⁴ C]-radioactivity excreted in faeces as percentage of the administered dose over the time interval from 0 to t ₂ (where t ₂ is the last quantifiable data point across all subjects)
fe _{urine, 0-t₂}	fraction of [¹⁴ C]-radioactivity excreted in urine as percentage of the administered dose over the time interval from 0 to t ₂ (where t ₂ is the last quantifiable data point across all subjects)
gCV	geometric coefficient of variation
gMean	Geometric mean
ICH	International Conference On Harmonisation
IPD	Important Protocol Deviation

Term	Definition / description
LLOQ	Lower limit of quantification
MedDRA	Medical Dictionary For Regulatory Activities
NOA	Not analysed
NOP	No peak detectible
NOR	No valid result
NOS	No sample available
PK	Pharmacokinetics
PKS	Pharmacokinetic parameter set
PR	Pulse Rate
PT	Preferred Term
Q1	Lower Quartile
Q3	Upper Quartile
SA	Statistical Analysis
SD	Standard Deviation
SOC	System Organ Class
TCM	Trial Clinical Monitor
ToC	Table of Contents
TMW	Trial Medical Writer
TS	Treated Set
TSAP	Trial Statistical Analysis Plan
ULN	Upper limit of normal range

3. INTRODUCTION

As per ICH E9 ([1](#)), the purpose of this document is to provide a more technical and detailed elaboration of the principal features of the analysis described in the protocol, and to include detailed procedures for executing the statistical analysis of the primary and secondary variables and other data.

This TSAP assumes familiarity with the CTP, including Protocol Amendments. In particular, the TSAP is based on the planned analysis specification as written in CTP Section 7 “Statistical Methods and Determination of Sample Size”. Therefore, TSAP readers may consult the CTP for more background information on the study, e.g., on study objectives, study design and population, treatments, definition of measurements and variables, planning of sample size, randomization.

Study data will be stored in a trial database within the Medidata Rave system.

The statistical analyses will be performed within the validated working environment CARE, including SASTM (current Version 9.4, by SAS Institute Inc., Cary, NC, USA), and a number of SASTM-based tools (e.g., macros for the analyses of AE data or laboratory data; Report Appendix Generator system (RAGe) for compilation/formatting of the CTR appendices).

PK parameters will be calculated using Phoenix WinNonlinTM software (version 6.3, Certara USA Inc., Princeton, NJ, USA).

4. CHANGES IN THE PLANNED ANALYSIS OF THE STUDY

All analyses described in this TSAP are in accordance with the statistical methods described in the CTP.

5. ENDPOINTS

5.1 PRIMARY ENDPOINTS

Primary endpoints are PK endpoints of mass balance recovery of [¹⁴C]-radioactivity as defined in Section 5.5.1.1 of the CTP:

- $fe_{urine, 0-t_2}$ (fraction of [¹⁴C]-radioactivity excreted in urine as percentage of the administered dose over the time interval from 0 to t_2 (where t_2 is the last quantifiable data point across all subjects))
- $fe_{faeces, 0-t_2}$ (fraction of [¹⁴C]-radioactivity excreted in faeces as percentage of the administered dose over the time interval from 0 to t_2 (where t_2 is the last quantifiable data point across all subjects))

CTP: Timeframe: *The timeframe for determination of these endpoints depends on excretion/recovery of radioactivity and may vary between 2-7 weeks, inclusive, after drug administration.*

5.2 SECONDARY ENDPOINTS

5.2.1 Key secondary endpoints

Not applicable

5.2.2 Secondary endpoints

Secondary PK endpoints will be defined as in Section 5.5.1.2 of the CTP for [¹⁴C]-radioactivity and BI 730357 in plasma:

- C_{max} (maximum measured concentration of the analyte)
- AUC_{0-t_2} (area under the concentration-time curve of the analyte over the time interval from 0 to the last quantifiable time point)

6. GENERAL ANALYSIS DEFINITIONS

6.1 TREATMENT

For basic study information on treatments to be administered, assignments of dose groups, and selection of doses, cf. Section 4 of the CTP.

All subjects were planned to be treated with a single dose of 50 mg BI 730357 BS (C-14) (BI 730357 mixed with [C-14]BI 730357 BS)

For statistical analysis of AEs, safety laboratory data and vital signs, the following analysis phases are defined for each subject:

Table 6.1: 1 Flow chart of analysis phases for statistical analyses of AEs, safety laboratory data and vital signs

Study analysis phase	Label	Start (inclusive)	End (exclusive)
Screening	Screening	Date of informed consent	Date/time of administration of study drug
On-treatment	BI 730357	Date/time of administration of study drug	12:00 a.m. on day after end of REP (REP ends 7 days after date of administration of study drug)
Follow-up	F/U	12:00 a.m. on day after end of REP	12:00 a.m. on day after trial completion date

CTR Section 15, Appendix 16.1.13.1.8.2 and Appendix 16.1.13.1.8.3 AE displays will present results for the on-treatment phase only. Appendix 16.1.13.1.8.1 will present results for the screening, on-treatment and follow-up phase.

Additionally, the following total will be provided in CTR Section 16.1.13.1.8.1 AE tables:

- "**Total**", defined as the total over all study phases (incl. screening, on-treatment, and follow-up)

6.2 IMPORTANT PROTOCOL DEVIATIONS

Consistency check listings (for identification of violations of time windows) and a list of protocol deviations (e.g. deviations in drug administration, in blood sampling times, etc.) will be provided to be discussed at the RPM/DBLM. At this meeting, it will be decided whether a discrepant data value can be used in analyses or whether it must be corrected in the clinical database. Each protocol deviation must be assessed to determine whether it is an IPD. For definition of IPDs, and for the process of identification of these, refer to the BI reference document "Identify and Manage Important Protocol Deviations (iPD)" (2).

If any IPDs are identified, they are to be summarised into categories and will be captured in the RPM/DBLM minutes via an Excel spreadsheet ([3](#)). The table below contains the categories which are considered to be IPDs in this trial. If the data show other IPDs, this table will be supplemented accordingly by the time of the RPM/DBLM.

IPDs will be summarised and listed.

Table 6.2: 1 Important protocol deviations

Category / Code	Description
A	Entrance criteria not met
A1	Inclusion criteria violated
A2	Exclusion criteria violated
B	Informed consent
B1	Informed consent not available
B2	Informed consent too late
C	Trial medication and randomisation
C1	Non-compliance
C2	Incorrect dose of trial medication
D	Concomitant medication
D1	Prohibited medication use
E	Missing data
	None ¹
G	Other trial specific important violations
G1	Certain violations of procedures used to measure primary or secondary PK data

Deviations C1, C2 and G1 can only be detected at the trial site.

¹ Missing visits, evaluations, and tests will be considered missing data, not IPDs

Source: BI reference document "Identify and Manage Important Protocol Deviations (iPD)" ([2](#)).

6.3 SUBJECT SETS ANALYSED

All entered subjects who received study medication will be included in the safety analysis and in the PK analysis depending on the availability of measurement values, and on their adherence to the CTP.

The following subject sets will be defined for statistical analysis:

- **Treated set (TS):**
This subject set includes all subjects who were documented to have received one dose of study drug. This is the full analysis set population in the sense of ICH-E9. It will be used for analysis of safety, demographic data and baseline characteristics.
- **Pharmacokinetic parameter analysis set (PKS):**
This subject set includes all subjects in the TS who provide at least one value for primary or secondary PK parameter that was not excluded because of iPDs relevant to

the statistical evaluation of PK endpoints as defined in Section 7.3 of the CTP. The discussion of all exceptional cases and problems and the decisions on the allocation of subjects to analysis sets will be made at latest at the RPM/DBLM

Table 6.3: 1 Subject sets analysed

Class of endpoint	Subject set	
	TS	PKS
Disposition	X	
Exposure	X	
IPDs	X	
Demographic/baseline data	X	
Safety parameters	X	
Primary PK endpoints		X
Secondary PK endpoints		X
Further PK endpoints		X

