7.3 PLANNED ANALYSES

Adherence to the protocol (such as inclusion/exclusion criteria, times of measurement, compliance with intake of trial medication, treatment dispensing errors, prohibited concomitant medication, completeness and consistency of data) will be checked. Important protocol deviations (iPDs) will be identified no later than in the Report Planning Meeting and provided in the TSAP.

Plasma/urine/faeces concentration data and parameters of a subject will be included in the statistical pharmacokinetic (PK) analyses if they are not flagged for exclusion due to a protocol deviation relevant to the evaluation of PK (to be decided no later than in the Report

Proprietary confidential information © 2018 Boehringer Ingelheim International GmbH or one or more of its affiliated companies

Planning Meeting) or due to PK non-evaluability (as revealed during data analysis, based on the criteria specified below). Exclusion of a subject's data will be documented in the CTR.

Relevant protocol deviations may be:

- Incorrect trial medication taken, i.e. the subject received at least one dose of trial medication the subject was not assigned to
- Incorrect dose of trial medication taken
- Use of restricted medications

Plasma, urine and faeces concentrations and/or parameters will be considered as non-evaluable, if for example

- a pre-dose concentration >5% of the C_{max} value of that subject
- missing samples/concentration data at important phases of PK disposition curve

The following subject and analysis sets will be defined for this trial:

Treated set (TS):

This subject set includes all subjects who were documented to have received one dose of study drug. This is the full analysis set population in the sense of ICH-E9.

PK analysis set (PKS):

The PK analysis set includes all subjects in the treated set who provide at least one value for primary or secondary PK endpoint and are not excluded according to the description above. Thus, a subject will be included in the PKS, even if he contributes only one PK endpoint value for the statistical assessment.

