7.3.5 Pharmacokinetic analyses

The pharmacokinetic parameters listed in [Section 5.5.1](#) will be calculated according to the BI SOP 'Standards and processes for analyses performed within Clinical Pharmacokinetics/Pharmacodynamics' [[001-MCS-36-472](#)].

Subjects who are not included in the PKS (refer to [Section 7.3](#)) will be reported with their individual plasma/urine/faeces concentrations and individual pharmacokinetic parameters; however, they will not be included in descriptive statistics for plasma/urine/faeces concentrations, pharmacokinetic parameters or other statistical assessment.

Only concentration values within the validated concentration range and actual sampling times will be used for the calculation of pharmacokinetic parameters. Concentrations used in the pharmacokinetic calculations will be in the same format provided in the bioanalytical report, (that is, to the same number of decimal places provided in the bioanalytical report).

The following descriptive statistics will be calculated for concentration-time data as well as for all pharmacokinetic parameters: number, arithmetic mean, standard deviation, minimum,

Proprietary confidential information © 2018 Boehringer Ingelheim International GmbH or one or more of its affiliated companies

median, maximum, arithmetic coefficient of variation, geometric mean, and geometric coefficient of variation. Descriptive statistics of pharmacokinetic parameters will be calculated using the individual values with the number of decimal places as provided by the evaluation program. Then the individual values as well as the descriptive statistics will be reported with three significant digits in the Clinical Trial Report.

If a pre-dose concentration value is greater than 5% of C_{max} , the subject's pharmacokinetic data will be not included in any statistical evaluations, in accordance with international guidances. The individual pharmacokinetic parameters of such a subject will be calculated and listed separately. If a pre-dose concentration is above BLQ, but less than or equal to 5% of the subject's C_{max} value, the subject's data without any adjustments will be included in all pharmacokinetic measurements and calculations.

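### Does the SAP's analysis set for the primary endpoints drop the protocol's non-evaluability ground for excluding PK data?

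*SAP*

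**What the plan says.** Protocol 7.3 leaves a subject's PK data out of the statistics for a protocol deviation relevant to PK, "or due to PK non-evaluability (as revealed during data analysis, based on the criteria specified below"). Its two examples of non-evaluability are a pre-dose concentration above 5% of the subject's Cmax, and "missing samples/concentration data at important phases of PK disposition curve". The PKS is then the treated subjects with at least one PK endpoint value who are not excluded on these grounds. The section adds that a single endpoint value is enough for membership.

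Protocol 7.3.5 makes the pre-dose rule firm: the subject's "pharmacokinetic data will be not included in any statistical evaluations, in accordance with international guidances". For subjects outside the PKS it says that "they will not be included in descriptive statistics for plasma/urine/faeces concentrations, pharmacokinetic parameters or other statistical assessment".

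SAP 6.3 requires "at least one value for primary or secondary PK parameter that was not excluded because of iPDs relevant to" the evaluation of the PK endpoints, citing protocol 7.3, and states that "decisions on the allocation of subjects to analysis sets will be made at latest at the RPM/DBLM". In SAP Table 6.2: 1 the missing-data category is empty, with the footnote "Missing visits, evaluations, and tests will be considered missing data, not IPDs". SAP 4 reads: "All analyses described in this TSAP are in accordance with the statistical methods described in the CTP".

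SAP 7.4 adds a value-level step. Each PK parameter carries an inclusion flag (APEXC) and each concentration carries another (ACEXC). Analyses on the PKS use only parameter values flagged as included.

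**The concern.** Read side by side, the two definitions of the set for the primary endpoints do not match. The protocol gives two grounds for exclusion and the SAP names one. Neither of the protocol's examples of non-evaluability is in the SAP's deviation table, and the footnote appears to close the route for missing samples. The SAP's deadline for allocating subjects also looks earlier than the protocol's allowance for problems found during data analysis. All this sits beside a statement that nothing has changed.

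With six subjects and a purely descriptive analysis, one man counts for a sixth of every summary. If a subject with an incomplete stool collection were kept with his recovery as measured, the mean and SD of faecal recovery would shift, and a reader could not tell which summary had been planned. A subject who vomits raises the same worry, because protocol 3.3.5 allows an additional subject so that six are evaluable.

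**Working it through.** The plan states no figure to reproduce, so the check is to apply both documents to the cases that could separate them.

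**1. Level of the rule.** Protocol 7.3 calls concentrations and parameters non-evaluable, not subjects. SAP 6.3 also works from values: a subject needs one that survives. The documents can disagree on membership only for a subject who loses every endpoint value.

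**2. Lost stool collection, plasma data intact.**
- Protocol: his faecal recovery may be judged non-evaluable. His Cmax and AUC stand, so he is in the PKS.
- SAP: his Cmax and AUC put him in the PKS. His faecal recovery can be flagged out under 7.4, which does not require a deviation for flagging.
- Category G1 in SAP Table 6.2: 1 (certain violations of PK measurement procedures) may also apply, since protocol 5.5.2.6 requires quantitative collection of all stools to 336 h.
- The footnote on missing data classifies deviations. It does not order that incomplete values be summarised.

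Result: the same membership, and the same summary available under both.

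**3. Pre-dose level above 5% of Cmax, no deviation.**
- Protocol 7.3.5: all his PK data leave the statistics.
- SAP 6.3 read literally: he is a PKS member. If all his values are flagged, he contributes nothing, and the summaries are those of the protocol.
- Likelihood: this is a single-dose, single-period trial. Exclusion criterion 12 bars investigational drug given in another trial within 60 days, or 60 × 24 = 1440 h. At the two half-lives in protocol Appendix 10.1 that is 1440/64 = 22.5 or 1440/28 = 51.4 half-lives. Criterion 23 separately limits earlier radiolabel studies.

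Result: a difference in label only, in a case that is unlikely to arise.

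**4. Timing.** The SAP's deadline covers allocation of subjects to sets. The protocol's allowance for findings during data analysis covers concentrations and parameters. The two can both be followed.

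**5. Vomiting.** It is not among the protocol's examples of non-evaluability. The list is open, so it could be judged so, but the SAP has removed no written protocol rule on it.

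**6. Size if an incomplete value were kept.** Appendix 10.1 gives a half-life of 64 h for total radioactivity and 86% faecal excretion. Assume mono-exponential excretion with no lag. The share of dose in day *i* is 86 × [exp(−24k(*i*−1)) − exp(−24k*i*)], with k = ln 2/64 per hour.

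| Day lost | Points of dose lost by the subject | Fall in mean, n = 6 |
|---|---|---|
| 1 | 19.7 | 3.3 |
| 2 | 15.2 | 2.5 |
| 3 | 11.7 | 2.0 |
| 6 | 5.4 | 0.9 |

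These figures show why flagging matters. They do not measure a difference between the documents. The no-lag assumption ignores gut transit and overstates day 1, and Appendix 10.1 itself describes elimination in more than one phase.

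**The case for a change.** The strongest argument for a change is that a set definition should stand on its own. The SAP's reference to protocol 7.3 qualifies the deviations, and 7.3 lists non-evaluability separately, so the reference does not restore the second ground. The flags could do the work, but the visible SAP gives no criteria for setting APEXC and does not mention the 5% rule. The sponsor's PK standard, which might supply both, is not in the documents. On the letter of SAP 6.3, a subject with a high pre-dose value and no deviation is in the PKS, while protocol 7.3.5 removes him from all statistics.

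The textual point stands: the SAP definition is narrower than the protocol's and should not have been. The inference that non-evaluable data would be summarised does not stand. SAP 3 bases the plan on protocol Section 7, so the criteria in 7.3 and 7.3.5 remain in force for whoever sets the flags. SAP 6.3 opens by making PK inclusion depend on available measurements and adherence to the protocol. Silence on the reasons for a flag is not an instruction to keep the value. It is also true that neither document settles how a vomiter's recovery is summarised. That is missing detail common to both, to be judged case by case with his individual values listed.

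**Conclusion.** No change is needed. SAP 6.3 has a drafting slip: it shortens the protocol's two exclusion grounds to one while SAP 4 declares accordance. An analyst following both documents would keep the same men in the PKS in the lost-stool case and could flag out the same values. The same summaries are available in the pre-dose case, where only the label of set membership differs. The effect on the reported statistics is zero if the flags in SAP 7.4 apply the protocol's criteria.

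This rests on two assumptions: that the flags are set by the criteria in protocol 7.3 and 7.3.5, and that the sponsor's PK standard, which is not available here, does not contradict them. The documents give no rate for lost collections, vomiting or high pre-dose values. With six subjects, individual values listed and no hypothesis test, any exclusion would be visible to the reader, and protocol 7.3 requires it to be documented in the trial report.
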